2.8 Serious adverse events

Incidence of venous thromboembolism and serious adverse events will be collected in this study to assess safety.

The proportion of participants experiencing a venous thromboembolism will be summarised by treatment arm and summaries of the time since randomisation will be presented. The number of readmissions will also be extracted from free text in SAE reports and will be summarised by treatment arm.

Serious adverse events coded as per the CTCAE will be summarised at the preferred term level and body system class. Events will be tabulated by treatment arm including information on the number with at least one event and the number of events to account for recurrent events.

Raw data for each SAE will be listed with information on event type, timing duration and outcome.

All above analysis will be undertaken for stage I and stage II

For stage II analysis we will also undertake the following analysis:

In addition, incident rate ratios for each event between treatment arms (RUX vs SOC or FOS vs SOC) with corresponding 95% CI will be calculated to account for differential follow-up and recurrent events with 95% CIs using a suitable model e.g. a negative binomial model or ZIP as appropriate. These results will be presented in both a table and graphically using a dot plot.

For events where time-to-event analysis is deemed appropriate we will present Kaplan-Meier plots with extended at risk tables for events that occur once within participants and mean cumulative function plots where events can recur within participants.^{1,2}

Blood measurements will be analysed as continuous outcomes calculating a mean difference and 95% CIs over the study follow-up period using a linear mixed effect model and the between arm effect will be plotted over time. Participants will be included as a random intercept with fixed effects for treatment arm, time and baseline outcome values. Stratification variables age and site, plus receipt of known effective treatments dexamethasone and/or tociluzimab, prior vaccination against COVID-19 and receipt of paxlovid and/or molnupiravir at the time of or prior to randomisation into MATIS will also be included as fixed effects. These outcomes will also be categorised as abnormal/normal and analysed using the distributional approach to retain power at day 14 and 28.3

3. Data analysis plan - Inferential analysis

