We will therefore explore the impact of RUX or FOS on the long term outcome from COVID-19 infection including overall survival and other co-morbidities such as VTE, diabetes, hypertension and long-COVID.

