#### **Secondary endpoints**

Comparison of the incidence, time-to-event, median or odds ratio of each of the parameters below at 14 and 28 days between RUX or FOS versus SOC:

- Mortality
- Invasive ventilation
- Non-invasive ventilation including CPAP and high flow nasal oxygen
- Renal replacement therapy
- Venous thromboembolism
- Inflammatory markers CRP, LDH, ferritin, D-dimer
- Serum creatinine
- Length of stay
- SSARs and discontinuations of study arms
- Change in severity on the modified WHO COVID-19 Ordinal Scale

Comparison of the incidence, time-to-event, median or odds ratio of each of the parameters below:

- Mortality at 3, 6, 12 & long term outcome
- Venous thromboembolism rate at 6, 12 and 18 months
- Renal replacement therapy at 6, 12 and 18 months
- Occurrence of new hypertension diagnosis
- Occurrence of new diabetes diagnosis
- Number of re-admissions within 12 months
- Causes of re-admissions in the last 12 months
- Occurrence of lung fibrosis
- Co-morbidities developed within 18 months post-discharge from hospital

Further secondary and exploratory objectives are not the focus of this study but maybe adopted using routine healthcare records (e.g. NHS Digital) and relevant research studies (e.g. UK Biobank and Genomics England). This will allow subsidiary analyses of the effect of the study treatments on particular non-fatal events (e.g. ascertained through linkage to Hospital Episode Statistics), the influence of pre-existing major co-morbidity (e.g. chronic heart, lung, kidney, liver disease, diabetes and use of immunosuppressive drugs) and longer-term outcomes (e.g. 6 month survival) as well as in particular sub-categories of patient (e.g. by genotype).

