#### 7.5 DOSE MODIFICATIONS FOR FOSTAMATINIB

**Table 4. Dose Adjustments for Fostamatinib** 

Hypertension	Recommended Action
Stage 1: systolic between 130-139 or diastolic between 80-89 mmHg	
 
Monitor, or initiate or increase dosage of antihypertensive medication for subjects with increased cardiovascular risk and adjust as needed until BP is controlled, in accordance with local standards.
 

Stage 2: systolic at least 140 or diastolic at least 90 mmHg	
 
Initiate or increase dosage of antihypertensive medication and adjust as needed until BP is controlled.
 

MATIS version 4.0 dated 2nd November 2022

IRAS: 282552 Page **34** of **57** 

Hypertensive crisis: systolic
over 180 and/or diastolic
over 120 mmHg

- Interrupt or discontinue study drug.
- Initiate or increase dosage of antihypertensive medication and adjust as needed until BP is controlled. If BP returns to less than the target BP, resume study drug at same daily dose.

Toxicity	Recommended Action
AST/ALT is 5 x ULN or higher and total BL is less than 2 x ULN	
 
Interrupt study drug.
 
Recheck LFTs every 72 hours:
 
If AST and ALT decrease, recheck until ALT and AST are no longer elevated (below 1.5xULN) and total BL remains less than 2xULN; resume study drug at next lower daily dose.
 
If AST/ALT persist at 5xULN or higher for 2 weeks or more, discontinue study drug.
 

AST/ALT is 3 x ULN or higher and less than 5 x ULN	
 
If patient is symptomatic (e.g., nausea, vomiting, abdominal pain):         
 
Interrupt study drug.
 
Recheck LFTs every 72 hours until ALT/AST values areno longer elevated (below 1.5 x ULN) and total BL remains less than 2 x ULN.
 
Resume study drug at next lower daily dose.
 
 
 

	If patient is asymptomatic:
	
 
Recheck LFTs every 72 hours until ALT/AST <1.5 x ULN) and total BL remains less than 2xULN.
 
Consider interruption or dose reduction of study drug if ALT/AST and TBL remain in this category (AST/ALT is 3 to 5 x ULN; and total BL remains less than 2 x ULN).
 
If interrupted, resume study drug at next lower daily dose when ALT/AST are no longer elevated (<1.5xULN) and total BL remains <2 x ULN.
 
If AST/ALT persist at 5 x ULN or higher for 2 weeks or more, discontinue study drug.
 

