AST/ALT is 3 x ULN or higher and total BL >2 x ULN	
 
Check direct and indirect BL levels. If direct BL is >2x ULN then discontinue study drug, if only indirect BL is >2x ULN then monitor as above.
 

Elevated unconjugated (indirect) BL in absence of other LFT abnormalities	
 
Continue study drug with frequent monitoring since isolated increase in unconjugated (indirect) BL may be due to UGT1A1 inhibition or the underlying disease.
 

Diarrhoea	
 
Manage diarrhoea using supportive measures (e.g., dietary changes, hydration and/or antidiarrheal medication) early after the onset until symptom(s) have resolved.
 
If symptom(s) become severe (Grade 3 or above), temporarily interrupt study drug.
 

MATIS version 4.0 dated 2nd November 2022

IRAS: 282552 Page **35** of **57** 

	
 
If diarrhoea improves to mild (Grade 1), resume study drug at the next lower daily dose.
 

Neutropenia	
 
If absolute neutrophil count decreases (ANC <1.0 x 109/L) (or is low at baseline) give G-CSF support to ensure NP> 1.0 x 109/L
 

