#### 7.16 TREATMENT DURATION

The planned duration of treatment is 14 days. Participants may be discontinued from treatment earlier due to unacceptable toxicity or disease progression which will be recorded as Serious Adverse Event (SAE). If participant is being discharged prior to day 14 they will go home and continue with the treatment plan.

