2.6 Adherence to allocated treatment and dose summaries

Please see section 2.6 in SAP I. This will be undertaken for stage I and stage II

All analysis of adherence data at the formal interim analysis will be completed by the independent statistician in Newcastle University to ensure the trial statistician remains blind and only DMC members will see these results.

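### The protocol foresees and manages blood-pressure rises on fostamatinib, but the supplied SAP compares them between arms only when they become serious adverse events (a minor gap, cheap to close)

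*SAP*

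**What the plan says.** Protocol 7.5, Table 4, begins its fostamatinib rules with hypertension and sets three bands: systolic 130-139 or diastolic 80-89 mmHg; systolic at least 140 or diastolic at least 90; and crisis, above 180 and/or above 120. For the middle band the instruction is "Initiate or increase dosage of antihypertensive medication and adjust as needed until BP is controlled". In crisis the site interrupts or discontinues the drug and treats the pressure, and the table continues: "If BP returns to less than the target BP, resume study drug at same daily dose".

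Protocol Table 7 and SAP Table 1 schedule vital signs and concomitant medications at screening, baseline and days 1, 7, 14 and 28. Protocol 7.14 requires medicines given after enrolment to be entered on the case report form. Neither schedule names blood pressure as an item.

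SAP 2.8 opens with "Incidence of venous thromboembolism and serious adverse events will be collected in this study to assess safety". It then plans readmission counts, SAE tables and rate ratios, and models for blood measurements.

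Three other places come close:
- Protocol 3.3 lists "Occurrence of new hypertension diagnosis" among the longer-term outcomes. Protocol 1.4 likewise puts "other co-morbidities such as VTE, diabetes, hypertension and long-COVID" under long-term follow-up.
- Protocol 7.16 allows treatment to stop early for "unacceptable toxicity or disease progression which will be recorded as Serious Adverse Event (SAE".
- SAP 2.6, on adherence and dose, says "Please see section 2.6 in SAP I". SAP 2.1 to 2.5 refer to that document in the same way.

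**The concern.** Evaluating the safety of both drugs is a secondary objective (Protocol 2.2). The effects that the protocol foresees for ruxolitinib are mainly haematological and hepatic, so they show up in blood tests, which SAP 2.8 models by arm. Fostamatinib's first-listed hazard is not a blood test and has no equivalent analysis. A site could follow Table 4 exactly, start antihypertensives and keep the patient on the drug, and that event would appear in no by-arm safety table in the supplied SAP.

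At stake is how completely the safety objective is answered. The planned outputs would not show how often pressure rose on fostamatinib relative to standard of care (SOC), and any comparison added later would be post hoc.

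**Working it through.** There is no figure in the plan to reproduce. The check is of the text, followed by arithmetic on what the missing table could show.

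**Text check: which planned output would show a rise?**

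| Event under Table 4 | Route into a by-arm safety table |
|---|---|
| Drug permanently stopped for unacceptable toxicity | SAE under Protocol 7.16, so SAP 2.8 tabulates it |
| Rise meeting an SAE definition in Protocol 8.1 | SAP 2.8 tabulates it |
| Crisis, drug interrupted, then resumed at the same dose | Protocol 7.16 does not make this an SAE; tabulated only if judged serious on other grounds |
| At least 140 or 90 mmHg, antihypertensive started, drug continued | None in the supplied SAP unless judged serious |
| 130-139 or 80-89 mmHg, monitored or treated | None in the supplied SAP unless judged serious |

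SAP 2.7 and 3.2 cover the WHO score and its components, thromboembolism, renal replacement, length of stay, inflammatory markers and creatinine. SAP 3.1.6 covers subgroups of the primary outcome. None analyses blood pressure, and none tabulates non-serious events. The protocol also disagrees with itself on recording non-serious events: section 8.5 says they are not recorded, while sections 8.4 and 11.4 say they are. Scheduled vital signs do not depend on that question.

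Diarrhoea has a similar gap (Table 4: "If symptom(s) become severe (Grade 3 or above), temporarily interrupt study drug"), but the visit schedule has no diarrhoea item, so existing data would not close it as simply.

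**Precision of the table that could be added**

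The documents give no rate of raised pressure, so the first calculation uses the widest case (50% in both arms). Half-width of the 95% CI for a risk difference with n readings per arm: 1.96 × √(0.25/n + 0.25/n).

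- n = 152 (full trial): 1.96 × √(0.5/152) = 11.2 points
- n = 144 (152 less 5%): 1.96 × √(0.5/144) = 11.5 points
- n = 76 (assuming half of 152 have a reading): 1.96 × √(0.5/76) = 15.9 points
- n = 57 (interim analysis): 1.96 × √(0.5/57) = 18.4 points

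Illustration with assumed rates of 10% on SOC and 20% on fostamatinib: 152 × 0.10 ≈ 15 patients against 152 × 0.20 ≈ 30. Half-width = 1.96 × √(0.09/152 + 0.16/152) = 7.9 points.

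Over a range of assumed SOC rates, 152 per arm gives 80% power (two-sided 5%) for about 10% vs 22%, 20% vs 34%, or 30% vs 46%.

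These figures describe the precision of the proposed table. They do not measure the harm done by its absence.

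**The case against.** The SAP largely follows the protocol's own choice. The safety endpoint in Protocol 3.3 is suspected serious adverse reactions and discontinuations, and Protocol 8.5 takes a seriousness-based approach suited to a pandemic trial. SAP 2.8 already goes further, with all SAEs, thromboembolism, readmissions and laboratory values. Protocol 10.3 gives the DMC interim analyses of all study data. Protocol 8.1 lets an event that needs intervention to avert a serious outcome be classed as serious, so some treated rises could reach the SAE tables. The schedule says only vital signs, and no case report form was supplied to show that systolic and diastolic values are entered.

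Most of this stands, and it is why the point is minor. It does not remove the gap. DMC review is confidential and is not a reported comparison. Following Table 4 requires blood pressure to be measured, but that does not prove that values reach the database, so the fix is conditional on capture.

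Three stronger readings are tempting, and the documents do not support them:
- *Hypertension on fostamatinib would go unreported altogether.* Serious cases and toxicity discontinuations are tabulated by arm.
- *Antihypertensive use is not summarised by arm.* SAP 2.4 (standard of care) and 2.6 (adherence and dose) defer to SAP I, which was not supplied and may cover drugs or interruptions.
- *The SAP dropped the new-hypertension endpoint.* The SAP is based on protocol 2.2 and describes main-study outcomes. The long-term follow-up sub-study came with version 3.0, so scope and version lag explain the absence. That endpoint would not measure on-treatment pressure in any case.

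**Conclusion.** The point holds as a minor improvement. In the supplied SAP, blood pressure is compared between arms only where a rise becomes an SAE, which leaves a foreseen, protocol-managed effect of fostamatinib largely out of the planned answer to the safety objective. The effect is on completeness of safety reporting only; no primary result, error rate or stopping rule changes.

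The conclusion assumes that blood measurements in SAP 2.8 means laboratory values, and that SAP I holds no blood-pressure comparison. The value of the fix assumes that systolic and diastolic readings are captured at scheduled visits. The 10% and 20% event rates, the other SOC rates in the power range and the 50% availability of readings are assumptions, and the documents support no particular size of effect.

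**What to change.** Add one paragraph and one table to SAP 2.8, labelled descriptive:

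1. From scheduled-visit vital signs, where systolic and diastolic values are captured, give the number and proportion per arm in each Table 4 band by visit, with baseline band and number with a reading. Assign each reading to its highest band, because the middle and crisis definitions overlap, and include a row for readings below all bands.
2. Give the risk difference with 95% CI for systolic at least 140 or diastolic at least 90 mmHg, fostamatinib vs SOC and ruxolitinib vs SOC.
3. State that SOC patients belong to the safety population. SAP 1.8 requires at least one dose of study medication, which read literally leaves no comparator.
4. If SAP I does not already do so, list antihypertensives started after randomisation by arm. Keep this apart from the pressure result and note that Table 4 directs such treatment in the fostamatinib arm only.

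The cost is small if the readings are in the database. Three limits should be written beside the table. Readings after discharge will be incomplete, and selectively so in patients who recover, although they continue the drug at home. Measurement and treatment are open label. Antihypertensive treatment hides part of any rise, so a null difference should not be read as reassurance.

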#### Dose reductions

Dose reductions or interruptions for non-haematological toxicity attributed to ruxolitinib are permitted in order to allow the patient to continue on the study. For haematological toxicity, the counts should be supported with blood product support ensuring that the platelet count remains  $> 50 \times 109$ /L. The dose of ruxolitinib may be reduced in response to certain toxicities as detailed below. Doses of supportive medications should be adjusted

according to standard practice. If absolute neutrophil count decreases (ANC  $<1.0 \times 109/L$ ) (or is low at baseline) give G-CSF support to ensure NP>  $1.0 \times 109/L$ 

Table 5. Management of decline in haematologic parameters

Parameter(s) at Time of Decline	Action
PLT < 50 x 10  /L	Transfuse platelets to ensure >50 x 109/L
ANC < 1.0 x 10  /L	Support with G-CSF to ensure NP> 1.0 x 109/L

In response to a decline in renal function (eGFR < 30ml/min) OR hepatic function (AST/ALT > 1.5 x ULN), the dose should be reduced by 50%, to be administered twice daily and patients should be carefully monitored. The dose can be re-escalated if eGFR subsequently increases above 30ml/min OR AST/ALT decreases to < 1.5 x ULN as applicable.

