# 7.10 BEST SUPPORTIVE THERAPY

All patients will receive best supportive therapy for COVID-19 as per physician's discretion.

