# 7.14 CONCOMITANT MEDICATION

The metabolism of ruxolitinib is affected by CYP3A4 inducers and inhibitors and dual inhibitors of CYP2C9 and CYP3A4 enzymes. Strict attention to this detail is required; please refer to permitted and prohibited concomitant medication as detailed in the SmPC. Patients should not receive any other JAK2 inhibitor whilst on the trial.

All medications, procedures, and significant non-drug therapies (including physical therapy and blood product support) administered after the participant was enrolled into the study must be recorded on the Case Report Forms. Each concomitant drug must be individually assessed against all exclusion criteria/prohibited medication.

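### SAP 2.8 compares blood counts without accounting for arm-specific G-CSF and platelet support, so haematological toxicity may be understated

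*SAP*

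**What the plan says.** **Support rules in the protocol.** For ruxolitinib, section 7.7 (Table 5) gives two actions: for platelets below 50 × 10⁹/L, "Transfuse platelets to ensure >50 x 109/L"; for neutrophils below 1.0 × 10⁹/L, "Support with G-CSF to ensure NP> 1.0 x 109/L". For fostamatinib, Table 4 has the neutrophil rule ("give G-CSF support to ensure NP> 1.0 x 109/L") but no platelet rule. In both drug sections the G-CSF instruction also covers a neutrophil count that is low at baseline. Standard of care has no count threshold; section 7.10 says: "All patients will receive best supportive therapy for COVID-19 as per physician's discretion".

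**Data available.** Protocol Table 7 schedules a full blood count at baseline and days 1, 7, 14 and 28. It is daily only for ruxolitinib patients on a strong CYP3A4 or dual CYP3A4/CYP2C9 inhibitor. Section 7.14 puts on the case report form: "All medications, procedures, and significant non-drug therapies (including physical therapy and blood product support) administered after the participant was enrolled".

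**Analysis.** For stage II, SAP 2.8 says: "Blood measurements will be analysed as continuous outcomes calculating a mean difference and 95% CIs over the study follow-up period". The model has a random intercept, the baseline value, age, site, vaccination and listed COVID-19 treatments. A second analysis classes the same measurements as abnormal or normal at days 14 and 28 by the distributional approach, without stating cut-offs. The measurements are not named; that they include neutrophils and platelets is inferred from the scheduled full blood count. SAP 1.9 names both counts, but only for the completed informal interim.

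**The concern.** Support changes the variable being compared, and the protocol makes its use depend on the arm. A ruxolitinib patient whose neutrophils fall below 1.0 is directed to G-CSF, and later samples then show a normal or high count. The mixed model takes those samples as they stand. The abnormal/normal analysis uses the same values, and by looking only at days 14 and 28 it can miss a low count at day 7 that was corrected by day 14.

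The low-at-baseline clause adds a second route. No exclusion criterion sets a minimum count. Of two patients who enter with the same low neutrophil count, the one on an active drug is directed to G-CSF and the one on standard of care is not. A baseline-adjusted model credits the resulting rise to the drug, even if the drug has no marrow effect.

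SAP 2.8 counts neither threshold crossings nor use of support. SAP 3.1.5 handles post-randomisation treatment, but only for the primary outcome and only for co-enrolment and COVID-19 therapies. At stake is whether the report shows how often counts fell far enough to need rescue.

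**Working it through.** The documents state no mean count, SD, cytopenia rate or support rate, so there is no figure to reproduce. From the documents come the thresholds (1.0 and 50), the visits and the maximum of 152 per arm. Every other value below is an assumption. Counts are in 10⁹/L.

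**1. Identity.** Observed difference = unsupported difference + f × r, where f is the excess share supported in the drug arm and r the mean rise that support produces. The sign changes only if f × r exceeds the size of the unsupported difference.

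**2. Neutrophils, only a few patients affected.** Assume log-normal counts, median 5, log-SD 0.5.
- Mean = 5 × e^0.125 = 5.67; SD = 5.67 × √(e^0.25 − 1) = 3.02; SE at 152 per arm = 3.02 × √(2/152) = 0.35.
- 5% fall to 0.7: 0.05 × (0.7 − 5.67) = −0.25.
- G-CSF lifts them to median 8 (log-SD 0.4, mean 8 × e^0.08 = 8.67): 0.05 × (8.67 − 5.67) = +0.15.
- Lift to median 15 (mean 16.25): 0.05 × (16.25 − 5.67) = +0.53.
- With 10% affected: −0.50 becomes +0.30 or +1.06.

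Here the sign turns as soon as the post-support mean exceeds that of unaffected patients. At 5% and median 8, however, both −0.25 and +0.15 lie within one SE.

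**3. Neutrophils, whole arm shifted.** Log-normal simulation: standard-of-care SD 3, drug-arm mean multiplied by a factor, support in the drug arm only. The last three columns give the difference after G-CSF lifts counts to the value shown.

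| SOC mean; factor; drug-arm CV | Share <1.0 | Unsupported | To 1.5 | To 10 | To 20 |
|---|---|---|---|---|---|
| 5; 0.8; 0.5 | 0.3% | −1.00 | −1.00 | −0.97 | −0.93 |
| 5; 0.7; 0.6 | 2.4% | −1.50 | −1.49 | −1.29 | −1.05 |
| 5; 0.6; 0.8 | 11.3% | −2.00 | −1.91 | −0.95 | +0.18 |
| 5; 0.5; 0.8 | 17.0% | −2.50 | −2.37 | −0.92 | +0.79 |
| 6; 0.5; 0.8 | 11.3% | −2.99 | −2.91 | −1.95 | −0.82 |

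Over all scenarios run (0.1% to 17% supported), the share of the difference lost was 0–5% for a lift to 1.5, 1–63% for a lift to 10 and 2–131% for a lift to 20. The sign changed only with a lift to 20 and at least 11% supported. For an unsupported difference of −1.0, break-even f is 1.0/10 = 10% for a rise of 10 and 1.0/20 = 5% for a rise of 20. It is unattainable for a rise of 0.7 (1.0/0.7 > 100%).

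**4. Platelets (ruxolitinib only).** Assume mean 250, SD 90; SE = 90 × √(2/152) = 10.3. If 5% (about 8 of 152) would sit at 30 unsupported, the shift is 0.05 × (30 − 250) = −11.0. Held at 60 it is 0.05 × (60 − 250) = −9.5. Support moves the mean by 1.5. With 0–22% transfused to 55–100, the simulation lost 0–9% of the difference and never changed sign. For a difference of −50, break-even f is 50/60 = 83% at a rise of 60 and above 100% at a rise of 30.

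**5. Low-count events.** In the same scenarios the share observed below threshold fell from as much as 17% (neutrophils) or 22% (platelets) to 0. This is a limiting case: it requires every analysed sample to follow successful support.

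**6. Trigger at a scheduled visit.** Take the 5% case of step 2 with the low value at day 7, the supported value (median 8) at day 14 and no effect at days 1 and 28. The visit differences are 0, −0.25, +0.15 and 0, averaging −0.10/4 = −0.025. The day 7 fall is in the data, and the average over follow-up nearly cancels it.

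**The case against.** The strongest reply is that comparing counts under drug plus directed support is a legitimate treatment-policy contrast, and that a low count found at a scheduled visit enters the model and would appear in the between-arm plot over time. Both points stand. But SAP 2.8 does not say that this contrast is intended, and as its only count analysis it does not show how many patients needed rescue.

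The serious adverse event route also recovers some cases. Protocol 8.1 allows events needing intervention to be judged serious, 7.16 records early stopping for unacceptable toxicity as an SAE, and 8.5 names bone marrow failure as an example reaction. SAP 2.8 tabulates and lists SAEs and gives rate ratios. Yet a neutropenia corrected with G-CSF is not automatically serious. Section 8.5 says non-serious events are not recorded, 8.4 and 11.4 say they are, and this SAP analyses none.

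Two limits remain. Support under standard of care is discretionary, not absent. SAP I, to which SAP 2.1 to 2.6 refer, was not supplied, so a descriptive table of support there cannot be excluded.

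A reader might infer that toxicity will be masked or reversed. The documents do not support that: they give no rates, and a change of sign needs the assumptions in steps 2 and 3. Nor is the mean count compared raw, since the model adjusts for baseline and covariates.

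**Conclusion.** The concern holds in limited form. Support is directed by arm, SAP 2.8 neither accounts for it nor reports its use, and the resulting bias runs towards no harm provided support is used more in the drug arms. The comparison with standard of care may therefore understate haematological toxicity, mainly for neutrophils and low-count events.

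The size is unknown. Under assumed values the loss in the mean neutrophil difference runs from negligible to complete. Reversal is possible only with a large G-CSF overshoot, combined either with a substantial supported share or with an effect confined to the few supported patients. For mean platelets the loss is 0–9% and reversal is not plausible; the weakness there is that a mean says little about rare deep falls. The finding also rests on the inference that neutrophils and platelets are among the unnamed blood measurements. It is worth correcting because the correction is cheap.

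**What to change.** Change SAP 2.8 only; no clinical rule is affected.

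- Name the haematology parameters and their cut-offs.
- Add, per arm with risk difference and 95% CI to day 28, the number of patients with neutrophils <1.0 or G-CSF, and with platelets <50 or platelet transfusion. Show each component separately.
- Base the count component on scheduled visits and show unscheduled or daily counts apart, because the daily counts in Protocol Table 7 apply only to some ruxolitinib patients.
- Report patients already below a threshold at baseline separately, or exclude them, so that baseline-triggered G-CSF is not counted as drug toxicity.
- Present the mixed model with and without values after first G-CSF or transfusion, and state that the version with them estimates the effect of drug plus support.

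The cost is SAP wording and a few derived variables from counts and concomitant treatments already to be recorded; no new data are needed. The downside is that support is partly discretionary in an open-label trial, so the support component may be inflated in the drug arms and should be read alongside the count component.
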